Title: Modulating Impulsivity in Suicidal Adolescents With Transcranial Direct Current Stimulation (tDCS)

NCT03365102

Latest approval date: 8/16/19

HUMAN RESEARCH PROTOCOL

Suicide is one of the leading causes of death in adolescence. To advance prevention and treatment efforts, there is a need for research in this area to move beyond identifying correlates or markers of suicidal risk to determining causal risk factors. The adoption of new experimental paradigms providing experimental control over candidate causal risk factors has been recommended as a means of meaningfully advancing the field. Impulsivity is a risk factor particularly relevant to adolescent suicidality. Although most studies linking impulsivity to suicidality examined impulsivity at the trait level, neuropsychological indices of this construct are state-sensitive, and thus may be more clinically meaningful insofar as they reflect proximal and modifiable risk rather than general risk for suicidal behavior.

One novel methodological paradigm that may hold promise in providing experimental control in the study of impulsivity is transcranial direct current stimulation (tDCS), a form of neurostimulation in which electrodes attached to the scalp deliver constant, low current stimulation to the brain. Although widely studied with adults, tDCS has rarely been applied in experiments with adolescents. Moreover, the mechanisms by which tDCS affects behavioral and cognitive impulsivity has not been adequately studied. One method to clarify the neural pathways underlying its effects is electroencephalography (EEG) and event-related potentials (ERPs).

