As a necessary first step in assessing state-sensitive impulsivity as a causal risk factor for suicidality, this study will assess the short-term effect of tDCS on impulsivity. That is, the researchers will evaluate the potential for tDCS to the right inferior frontal gyrus (rIFG) and left orbitofrontal cortex (IOFC) to modulate behavioral and cognitive impulsivity, respectively, in adolescent suicide attempters. Adolescents in a psychiatric hospital program will be enrolled if they attempted suicide prior to their admission and who had made an impulsive attempt as measured on the C-SSRS (attempt initiated within a day of thinking of it). Participants will be randomized to receive either anodal tDCS to the rIFG, anodal tDCS to the IOFC. Randomization will occur through a computer program (like flipping a coin with participants having an equal chance of being in each group). This will occur after we determine if the participant is eligible for the study. There will be 20 participants in each group. Participants will not be told which group they are randomized into. Baseline impulsivity measures will be re-given after tDCS or sham stimulation to assess changes in impulsivity. Additionally, EEG/ERP data will be collected during the impulsivity tasks, and resting-state EEG data will be collected pre- and post-tDCS.

Participants Adolescents (N = 60) between the ages of 13 and 17 who have been admitted to an adolescent psychiatric hospital (inpatient or partial). Adolescents will be eligible to participate if they: (i) have attempted suicide prior to admission; (ii) had made an impulsive attempt as measured on the C-SSRS (attempt initiated within an hour of thinking of it); (iii) speak and read English fluently, (iv) have no significant cognitive disability based on a standard psychiatric exam, and (v) are not actively psychotic.

Exclusion criteria are: (i) a significant general medical or neurological condition; (ii) history of seizure, head injury, brain surgery or tumor; (iii) intracranial metallic implants or implanted electrical devices; (iv) substance abuse or dependence in the past six months.

Sample Availability. Hospital admission data suggests more than 60 adolescents would meet these study criteria over the two year recruitment period. We have found in other studies recruiting from this site to allow for adequate time for in-depth assessment batteries larger than that of the proposed study.

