Two Choice Impulsivity Paradigm (TCIP; Dougherty et al., 2003): The TCIP will be used as a delay discounting task (DDT) to assess impulsive choice, which requires participants to choose between immediate but small rewards and delayed but larger rewards over 50 trials. Delay discounting (or impulsive choice), is the tendency to undervalue an anticipated future reward as the time delay to obtaining the reward increases. A higher discounting rate (i.e., preference for smaller immediate rewards over larger delayed rewards) is viewed as reflecting greater cognitive impulsivity.

Stop-Signal Task (SST; Hamilton et al., 2015): The SST will be used to assess behavioral impulsivity. The SST requires participants to respond to a target stimulus as quickly and accurately as possible by pressing a button, but also to withhold their response when they hear an auditory signal. Thus, this task involves a competition between activating and inhibiting processes.

iv. **tDCS and EEG.** tDCS will be applied and EEG recordings made using a starstim/enobio device, with stimulation and recording electrodes located inside the cap. This device provides the user with up to 8 stimulating electrodes that can be programmed through software to be either anodal or cathodal in polarity and up to 32 recording electrodes. When not being used for stimulation, the 8 stimulating electrodes can also be used for recording, allowing for a total of 40 electrodes to be used for recording EEG pre- and post-stimulation. As in past studies, electrodes will be placed according to standard 10-10 coordinates corresponding to the rIFG (anode over F8 and cathode over FP1), which has been associated with behavioral impulsivity, and the IOFC (anode over FP1 and cathode over FP2), which has been linked with cognitive impulsivity.

Data analysis

Aim	Hypothesis	Dependent	Independent†	Analysis	MDE‡
1	H1	SST	tDCS/rIFG, time, tDCS/rIFG×time	GLM (repeated-measures ANOVA)	d=0.35
2	H2	SST	As above, plus reduced theta power (EEG), increased P3 (ERP)	As above with effects for EEG and ERP added; change in tDCS parameter estimate informs mediation	r=0.35
EA	EH1	DDT	tDCS/IOFC, time, tDCS/IOFC×time	GLM (repeated-measures ANOVA)	d=0.35
	EH2	DDT	As above, plus reduced VLFO (EEG), reduced SCPs (ERP)	As above with effects for EEG and ERP added; change in tDCS	r=0.35

† All analyses will include PROMIS (depressive symptoms) and Connor-3 (ADHD symptoms) as covariates

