‡ MDE minimal detectable effect, expressed as standardized mean difference (Cohen's d) for aim 1 and minimal detectable correlation for aim 2 (n=60), assuming type-I error level 5% and type-II error level 20%. Repeated-measures ANOVA assumes correlation of 0.9 of repeated measures.

Protection of Human Subjects

Source of Research Material

Adolescents will complete interviews, self-report measures, computer tasks, EEG testing, and tDCS. The data will be obtained for research purposes.

Recruitment and Consent

Parents and adolescents will be contacted about participating in the study after their medical records have been reviewed upon admission to Bradley, Butler or Hasbro. Medical charts will be reviewed by trained members of the research team familiar with the study criteria. These study staff will coordinate with treatment providers to arrange times to meet with potentially eligible patients and their parents in person. The staff will present and explain the study to the adolescent patient and his or her parent at Bradley, answer any questions they may have, and, if appropriate, present and explain the consent forms. All patients and parents will be fully informed of the purposes and procedures of the study. PI [name] will train the research staff in the steps necessary to obtain consent. All participants and parents will be fully informed about the purpose and procedures of the study both verbally and through a written description contained in the assent/consent forms. PI [name] and other study staff will be responsible for soliciting and obtaining informed consent/assent after any questions have been addressed. All participants will be required to provide assent and their parents or guardians to sign an informed consent document in order to participate in the study. Patients will be provided with a copy of the consent document, and the original will be placed in the PHI filing cabinet.

Potential Risk

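### No planned model has an EEG or ERP measure as its outcome, so the randomised effect of tDCS on theta, P3, VLFO and SCPs is never estimated, and the change in the tDCS coefficient cannot stand in for it

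*Combined protocol and SAP*

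**What the plan says.** The opening background gives the reason for recording brain activity: "One method to clarify the neural pathways underlying its effects is electroencephalography (EEG) and event-related potentials (ERPs"). The study overview says that EEG/ERP data are collected during the impulsivity tasks, which are given before and after stimulation, and that "resting-state EEG data will be collected pre- and post-tDCS".

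The Data analysis table has four rows:

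| Row | Dependent | EEG/ERP measures | Where they appear |
|---|---|---|---|
| H1 | SST | none | – |
| H2 | SST | theta power, P3 | Independent column |
| EH1 | DDT | none | – |
| EH2 | DDT | VLFO, SCPs | Independent column |

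The H1 terms are "tDCS/rIFG, time, tDCS/rIFG×time". H2 takes these terms and adds the brain measures: "As above, plus reduced theta power (EEG), increased P3 (ERP"). EH2 does the same: "As above, plus reduced VLFO (EEG), reduced SCPs (ERP"). The H2 analysis cell reads "As above with effects for EEG and ERP added; change in tDCS parameter estimate informs mediation". The corresponding EH2 cell is cut off in the available text. A footnote adds: "All analyses will include PROMIS (depressive symptoms) and Connor-3 (ADHD symptoms) as covariates". The Aim 2 detectable effect is r=0.35, described as "minimal detectable correlation for aim 2 (n=60), assuming type-I error level 5% and type-II error level 20"%.

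**The concern.** The words reduced and increased describe what stimulation is expected to do to each brain measure. A measure in the predictor column cannot test that; it has to be an outcome. The effect of tDCS on theta or P3 is also the link in Aim 2 that randomisation protects, whereas the link from theta or P3 to SST is observational even in a randomised trial. The plan models the second link and omits the first.

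The statistic it relies on instead, the change in the tDCS estimate, merges the paths through both measures into one number. Aim 2 could then be reported as showing mediation without any estimate of whether theta fell or P3 rose. It could also be reported as showing none when both moved as expected. This is a different matter from whether the change has a test or an interval: a perfectly estimated sum would still leave the directional part of H2 unanswered.

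**Working it through.** **1. The plan's own figures.**
- Aim 2, Fisher z, two-sided 5%, 80% power, n=60: r = tanh((1.960 + 0.842)/√57) = 0.355. The stated r=0.35 reproduces. It is a detectable correlation, not a detectable difference between arms on a brain measure.
- Aim 1, noncentral t on change scores, with SD factor √(2(1−0.9)) = 0.447: the detectable difference for 20 v 40 is 0.780 change-score SDs, and 0.780 × 0.447 = 0.349. The stated d=0.35 reproduces for one active arm against the other two arms pooled. For 20 v 20 (active against sham), 0.909 × 0.447 = 0.407.

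Neither figure is in dispute.

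**2. What the change in the tDCS estimate contains.** Assume that the arm-by-time effect is analysed as a comparison of change scores, that theta and P3 enter together as change scores, and that the covariates are the same with and without them. Let a be the effect of tDCS on a measure and b that measure's slope on SST. Least squares then gives exactly

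change = c − c′ = a_theta × b_theta + a_P3 × b_P3,

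where c and c′ are the tDCS estimates without and with the two measures. The planned models estimate c, c′ and both b. They do not estimate either a.

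The identity was checked on one simulated data set (n=60, 20 v 40, two covariates): c = −0.943 and c′ = −0.568, a change of −0.374, with a_theta = −0.66 and a_P3 = +0.63. Reversing the scale of theta, P3 or both reverses a and b together and leaves c, c′ and the change identical.

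**3. Different patterns, same change.** The inputs are illustrative, in change-score SD units, with SST residual SD 1 and a direct tDCS effect of −0.4:

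| Pattern | a_theta | b_theta | a_P3 | b_P3 | Sum |
|---|---|---|---|---|---|
| Theta down, P3 up (hypothesised) | −0.9 | 0.3 | 0.9 | −0.3 | −0.54 |
| P3 only | 0 | 0.3 | 0.9 | −0.6 | −0.54 |
| Theta up only | 0.9 | −0.6 | 0 | −0.3 | −0.54 |
| Theta up, P3 down, slopes also reversed | 0.9 | −0.3 | −0.9 | 0.3 | −0.54 |
| Theta up, P3 down, slopes as in row 1 | 0.9 | 0.3 | −0.9 | −0.3 | +0.54 |
| As hypothesised, offsetting slopes | −0.9 | 0.3 | 0.9 | 0.3 | 0 |

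Simulation (20 v 20, 4,000 runs per pattern) gives mean changes within 0.01 of these sums. The slopes differ between rows, and the equality in the first four depends on that.

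Fixing the slopes does not identify the two a-paths either. With b_theta = 0.4 and b_P3 = −0.4, the pairs (a_theta, a_P3) = (−0.8, 0.8), (0.4, 2.0) and (−2.0, −0.4) all give −0.64.

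**4. What a direct test could detect.** The documents give no pre-post correlation for any EEG/ERP measure. The 0.9 is stated for the repeated-measures ANOVA, which the table applies to SST and DDT. Taking 0.5 to 0.9 as an assumed range (two-sided 5%, 80% power):

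| Pre-post correlation | 20 v 40 | 20 v 20 |
|---|---|---|
| 0.9 | d = 0.35 | d = 0.41 |
| 0.7 | d = 0.60 | d = 0.70 |
| 0.5 | d = 0.78 | d = 0.91 |

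At the 2.5% level, the first Holm step for two tests, the values at correlation 0.9 are about 0.39 and 0.45.

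**The case against.** Several points on the other side stand.

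- **The slopes are in the planned output.** A reader might infer that the H2 rule cannot distinguish the hypothesised pattern from its opposite. That goes too far. If only the tDCS effects on theta and P3 reverse, the change switches from −0.54 to +0.54 and the total tDCS effect moves from −0.94 to +0.14 (−0.4 − 0.54 against −0.4 + 0.54). The change stays the same only if the slopes on SST reverse too, and in the simulation each nonzero slope had the right sign in about 96% of runs or more. The offsetting case would show in the slopes as well. What remains is that the a-paths have no estimate or test, and one sum cannot be split between two measures.
- **Aim 2 does not depend on H1.** A reader might infer that a null H1 leaves Aim 2 with nothing to report. The identity says otherwise: with a direct effect of +0.54 and the measures as hypothesised, the total effect is 0 and the change is still −0.54.
- **The wording is loose.** The cell says that the change informs mediation, which is not a decision rule. The hypotheses are not written out in the available text, so the directions come from the table labels. Joint entry of both measures is the natural reading but is not stated. The EH2 rule is cut off, so the argument about the rule rests on H2.
- **A direct test may be weak.** For a raw d of 0.40 at 20 v 20, power is about 79% at correlation 0.9 but 36% at 0.7 and about 23% at 0.5.

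None of this supplies a model with an EEG or ERP outcome.

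**Conclusion.** The concern holds in a bounded form. No planned model in the available text estimates or tests the randomised effect of tDCS on theta power, P3, VLFO or SCPs. This follows from the table alone and needs no simulation. For H2, the change in the tDCS estimate is the sum of two products. By itself it shows neither the direction of the tDCS effect on each measure nor each measure's share. It is unchanged when a measure's tDCS effect and its slope both reverse, and it can be near zero when tDCS moves both measures as labelled.

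The algebra assumes a least-squares analysis of change scores with both measures entered together. The −0.54 values are illustrative, not predictions. H1 and EH1 are unaffected. The point should be corrected because EEG/ERP is included to study mechanism, and the randomised part of that question has no planned analysis.

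**What to change.** - Add rows to the analysis table with theta power and P3 (Aim 2) and VLFO and SCPs (exploratory aim) as dependent variables. Use the same arm, time and arm-by-time terms and the same covariates as H1 and EH1.
- Take the arm-by-time estimate, with its confidence interval and test, as the evidence for the directional part of H2 and EH2. Adjust the two Aim 2 tests for multiplicity, for example by Holm.
- Do not call a measure a mediator in the hypothesised direction on the sign of the estimate alone: with no true effect, that condition is met about half the time.
- Report the change in the tDCS-by-time estimate for each measure separately as well as jointly, with the slopes.
- State the detectable effect for the new models over a range of pre-post correlations, since 0.9 is not supported for EEG/ERP.

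The cost is SAP wording, four extra models and two more Aim 2 tests, on data already being collected, with no extra participants or procedures. The downside is limited precision, so a non-significant arm-by-time result should be read through its interval and not as absence of an effect.

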After completing these assessments, participants will be randomly assigned to receive either anodal tDCS to rIFG, anodal tDCS to IOFC, or sham stimulation. tDCS at a constant current of 1.5 mA and sham stimulation will be applied for one 20-minute session. In the sham condition, the current will be ramped up to 1.5mA for 30 seconds and then ramped back down to 0. As this commonly used sham procedure produces a brief tingling sensation, participants are kept unaware of their experimental condition. Prior to and tDCS, participants will complete the SST and TCIP, while EEG is recorded to extract ERPs in a single-blind procedure. The participants and PI [name] will be blind to experimental condition, but Co-I [name] will not be blinded. Resting-state EEG, for 5 minutes, will be recorded before pre-stimulation tasks and after post-stimulation tasks. These tasks were specifically chosen because they can be administered well within an hour, the approximate duration of effect from a single-session of tDCS. The side effects questionnaire will be administered following the tDCS session. Ordering of tasks will be counterbalanced. These assessments will take about 3.5 hours total and they will be audio recorded for supervision and training purposes with participants' permission. They will take place in an interview room in the hospital, outside of any clinical care. Adolescent participants and parents will be paid \$100 and \$25, respectively, upon completion of the study.

Assessment Measures.

i. Self-report measures

Wechsler Abbreviated Scale of Intelligence (WASI; Wechsler, 1999): The WASI uses vocabulary, similarities, block design, and matrix reasoning subtests similar to those of the WAIS to provide an estimate of full scale IQ in approximately 30 minutes.

Depressive symptoms will be assessed using the pediatric version of the PROMIS depression scale. Higher scores reflect greater symptom severity.

The Conners-3 Self-Report (Conners-3 SR; Kollins, Epstein, & Conners, 2004): Current ADHD symptoms will be assessed with the Conners-3, with higher scores reflecting greater severity. ADHD will be a covariate in all analyses, as impulsivity is a hallmark of this disorder.

Suicidal ideation will be measured using the Passive and Active Suicidal Ideation Scale (PASIS). Higher scores reflect greater severity of ideation.

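### Aim 2 (H2) judges mediation by a change in the tDCS estimate with no interval or test; at n=60 that change alone cannot separate partial mediation from chance

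*Combined protocol and SAP*

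**What the plan says.** The Aim 1 row of the Data analysis table fits a repeated-measures ANOVA of the SST on tDCS/rIFG, time and their interaction. The H2 row keeps that model and lists as independents "As above, plus reduced theta power (EEG), increased P3 (ERP"). The analysis cell reads "As above with effects for EEG and ERP added; change in tDCS parameter estimate informs mediation". A footnote adds that "All analyses will include PROMIS (depressive symptoms) and Connor-3 (ADHD symptoms) as covariates".

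The only power figure for H2 is r=0.35, which the second footnote describes as the "minimal detectable correlation for aim 2 (n=60"), at 5% type-I and 20% type-II error. The same footnote says "Repeated-measures ANOVA assumes correlation of 0.9 of repeated measures", which bears on the d=0.35 given for Aim 1.

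On design, the overview says "There will be 20 participants in each group", with three arms and N=60. The paragraph on randomisation and stimulation, just before Assessment Measures, describes two EEG sources. One is during the tasks: "participants will complete the SST and TCIP, while EEG is recorded to extract ERPs in a single-blind procedure". The other is at rest: "Resting-state EEG, for 5 minutes, will be recorded before pre-stimulation tasks and after post-stimulation tasks".

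**The concern.** Aim 2 is the mechanistic aim, and its whole decision rule is one clause. Three things needed to apply it are missing.

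- **Uncertainty.** There is no standard error, interval, test or threshold for the change, so a reader cannot judge whether an observed change exceeds what chance would give with 60 participants.
- **Coefficient and mediator coding.** The carried-over model holds both a tDCS term and a tDCS×time term, and the row does not say which one is to be watched. Nor does it say whether theta and P3 enter as post-stimulation values, as changes, as time-varying values, or crossed with time. The choice matters: under one coding tDCS×time cannot move at all.
- **Source of theta.** P3 can be tied to the task recordings, because the stated purpose of task EEG is ERP extraction. Nothing assigns theta to task or resting EEG.

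At stake is whether Aim 2 can be interpreted. Half mediation could be read as none, or a chance shift as a mechanism. Aim 1 is not affected.

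**Working it through.** **1. The plan's own figures.** Two-sided 5% (sidedness is not stated) and 80% power give 1.960 + 0.842 = 2.802.

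- One correlation, n=60, Fisher z: tanh(2.802/√57) = tanh(0.371) = 0.355. The stated r=0.35 reproduces.
- tDCS×time, correlation 0.9: 2.802 × √(2 × (1 − 0.9)) × √(1/n₁ + 1/n₂).
  - 20 v 40: 2.802 × 0.447 × 0.274 = 0.343 (t-based 0.349).
  - 20 v 20: 2.802 × 0.447 × 0.316 = 0.396 (t-based 0.407).
  - 20 v 20 one-sided: 2.486 × 0.447 × 0.316 = 0.352 (t-based 0.358).
- tDCS main effect, 20 v 40: t-based 0.760.

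So d=0.35 points to tDCS×time rather than the main effect. It fits 20 v 40 best if testing is two-sided, but a one-sided 20 v 20 comparison fits nearly as well. The contrast is an inference.

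**2. Is the change in estimate a valid quantity?** With the same participants and covariates in every linear equation, let c be the tDCS effect without mediators and c′ the effect with them. Then c − c′ = a₁b₁ + a₂b₂, where a is the effect of tDCS on each mediator and b the effect of each mediator on SST given tDCS. A numerical check with two mediators and n=60 agrees to rounding error. The rule estimates the right thing; what is missing is its uncertainty.

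**3. How noisy is it at n=60?** Simulation, 6,000 runs. From the plan: n=60, total effect 0.35 (negative sign means less impulsivity), PROMIS and Conners-3 in the model. Assumed: 20 v 40, pre-post correlations 0.90 to 0.92, a 0.6 SD shift in each mediator, time-varying entry.

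| True state | 2.5th to 97.5th percentile of c − c′ |
|---|---|
| No mediation | -0.156 to +0.151 |
| Half mediation | -0.354 to -0.027 |
| Complete mediation | -0.574 to -0.163 |

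A repeat simulation gave about -0.18 to +0.17, -0.37 to -0.01 and -0.57 to -0.18.

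From the half-mediation percentiles, the midpoint is -0.1905 and the SD about (0.354 − 0.027)/3.92 = 0.083. By normal approximation, the share of half-mediation trials beyond the no-mediation 2.5th percentile is Φ((−0.156 + 0.1905)/0.083) ≈ 66%. The other third or so look like no mediation.

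**4. Does mediator coding matter?** Large simulated sample (N=60,000, 1:2, assumed 0.8 SD shifts, complete mediation):

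| Model | tDCS×time |
|---|---|
| No mediators | -0.402 |
| Mediators constant over time, not crossed with time | -0.402 |
| Time-varying mediators | -0.001 |
| Mediator change × time | -0.003 |

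The second line is algebra: with complete data at two time points, a term with the same value at both cannot alter a pre-post difference.

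**5. What does r=0.35 imply for mediation?** The plan gives no path sizes, so this is illustrative. Assume a partial correlation of 0.35 on both paths, one mediator and no covariates, and require both paths to be significant at two-sided 5%. Power is about 64% at 20 v 40 and about 37% at 20 v 20.

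**6. Timing.** Post-stimulation resting EEG is recorded after the post-stimulation tasks, so it cannot precede the SST outcome. Task EEG is concurrent with it. Neither source gives a mediator measured before the outcome.

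**The case against.** The strongest reply is that the rule is not a wrong method. The change in coefficient equals the summed indirect effects, so only an interval is missing. The plan says the change informs mediation and presents the study as a first step; it does not promise formal proof. All of this stands, and it rules out the stronger claim that the planned rule can say nothing about mediation: complete mediation is largely distinguishable from none even without an interval.

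A reader might also infer that H2 is bound to return a null result because time-constant mediators cannot move tDCS×time. The documents do not support that. The table speaks of reduced theta and increased P3, EEG is recorded before and after stimulation, and usual repeated-measures software crosses a between-subject covariate with time. The time-constant coding is possible but not the likeliest reading. What stands against the plan is that the coding is unstated.

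Nor is r=0.35 an error: it reproduces and is labelled as a correlation. And the documents do not favour task over resting EEG for theta, so it would be preference to impose one.

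Finally, the noise and power figures rest on assumed mediator shifts, path sizes and contrast. That is so, but the absence of an interval is plain from the text and does not depend on them.

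**Conclusion.** The concern holds in a limited form. H2 uses a valid point estimate with no measure of its uncertainty, and leaves the coefficient, contrast, mediator coding and theta source open. Under the stated assumptions, the 95% ranges for no mediation and half mediation overlap between about -0.16 and -0.03, and about a third of half-mediation trials fall inside the no-mediation range. Partial mediation therefore cannot be told from chance by the change alone. The ranges would shift with other mediator shifts or with a 20 v 20 contrast.

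This should be fixed before analysis because it decides whether Aim 2 can be interpreted. It does not show that the planned analysis would fail, that the footnote is miscalculated, or that 20 v 40 is the intended contrast. Whether it extends to EH2 cannot be settled, because that analysis cell is cut off in the available text.

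**What to change.** 1. State that the mediated effect is the one on tDCS×time, or equivalently the baseline-adjusted difference in post-stimulation SST, and state the contrast. Enter theta and P3 as post-stimulation values adjusted for baseline, or as changes crossed with time.
2. Report the indirect effect a×b for theta and for P3, adjusted for both baseline mediators, baseline SST, PROMIS and Conners-3, together with the total change in estimate. Use the same covariates in every equation so that the parts add up to the total. Give each a bootstrap 95% confidence interval and base the mediation conclusion on the intervals. In simulation of a closely similar bootstrap analysis at n=60 (20 v 40), the interval excluded zero in 3.9 to 4.8% of trials when path b was zero, with 93 to 96% coverage.
3. Name the recording that supplies theta. Say that post-stimulation resting EEG follows the tasks, that task EEG is concurrent with them, and that path b is not randomised, so mediation findings are suggestive.
4. Keep r=0.35 as the single-correlation figure and add that it is not power for mediation. If a mediation power figure is given, mark it as illustrative and show both 20 v 40 and 20 v 20.
5. Apply the same to EH2 only if its full cell states the same rule.

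The cost is SAP wording, slightly more analysis and a more cautious Aim 2 conclusion. No new data or participants are needed.

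### The MDE of d=0.35 names neither comparator nor sidedness; a two-sided test of active v sham (20 v 20) has an MDE of 0.40–0.41 and 67–68% power at d=0.35

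*Combined protocol and SAP*

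**What the plan says.** The section on consenting and screening randomises participants to tDCS over the rIFG, tDCS over the IOFC, or sham. The study overview gives the group size, "There will be 20 participants in each group", a total of 60, and the purpose of repeating the tasks: "Baseline impulsivity measures will be re-given after tDCS or sham stimulation to assess changes in impulsivity".

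In the Data analysis table, the model terms for H1 (stop-signal task) are "tDCS/rIFG, time, tDCS/rIFG×time". Those for EH1 (delay discounting) are "tDCS/IOFC, time, tDCS/IOFC×time". Both are to be fitted by repeated-measures ANOVA, and both carry an MDE of d=0.35. For H2 the table says "As above with effects for EEG and ERP added; change in tDCS parameter estimate informs mediation", with an MDE of r=0.35. Footnote † adds: "All analyses will include PROMIS (depressive symptoms) and Connor-3 (ADHD symptoms) as covariates".

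Footnote ‡ defines the MDE as "MDE minimal detectable effect, expressed as standardized mean difference (Cohen's d) for aim 1 and minimal detectable correlation for aim 2 (n=60"), sets the error levels by "assuming type-I error level 5% and type-II error level 20" percent, and assumes a correlation of 0.9 for the repeated-measures ANOVA. Sham appears neither in the table nor in its footnotes.

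**The concern.** With three arms, a single indicator for one active site leaves the reference group open: sham alone (20 v 20), or sham plus the other active arm (20 v 40). Sidedness is open too. These choices change both the power and the quantity being tested.

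If H1 and EH1 are two-sided tests against sham, the stated 80% power at d=0.35 is not delivered. If the indicator is fitted to all 60, the power is there but the comparison is no longer with sham. H2 and EH2 inherit the problem, because they build on the same models and H2 judges mediation by how the tDCS estimate changes.

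**Working it through.** **Inputs.** 20 per arm and three arms (study overview; consenting and screening section). 5% type-I error, 80% power and correlation ρ=0.9 (footnote ‡). No dropout allowance and no covariate R² are stated, so both are taken as zero.

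**Method.** With two time points, the group×time test is a two-sample t-test on change. In units of the single-occasion SD, the variance of change is 2(1−ρ) = 2(1−0.9) = 0.2, and SE = √[0.2(1/n₁+1/n₂)].

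- 20 v 20: SE = √(0.2×0.100) = 0.1414
- 20 v 40: SE = √(0.2×0.075) = 0.1225

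The MDE is the d giving 80% power under the noncentral t.

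**Which tests reproduce 0.35?**

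| Comparison | Sides | Error df | MDE | Power at d=0.35 |
|---|---|---|---|---|
| One active arm v other 40 | two | 58 | 0.349 | 80.2% |
| Active v sham, 20 v 20 | two | 38 | 0.407 | 67.4% |
| Same, three-arm error term | two | 57 | 0.403 | 68.2% |
| Active v sham, 20 v 20 | one | 38 | 0.358 | 78.4% |
| Same, three-arm error term | one | 57 | 0.356 | 78.8% |

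So 0.35 fits two-sided 20 v 40 or, roughly, one-sided 20 v 20. It does not fit two-sided 20 v 20.

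**Which reading do the plan's other figures favour?** Footnote ‡ applies one type-I error to both MDEs. For a correlation, the Fisher approximation gives MDE = tanh[(z_α+z_β)/√(n−3)].

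- n=60, two-sided: tanh(2.802/√57) = 0.355
- n=60, one-sided: tanh(2.486/√57) = 0.318
- n=40 (one active arm plus sham): 0.431 two-sided, 0.387 one-sided

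The stated r=0.35 fits a two-sided test in all 60. The Aim 2 model is the Aim 1 model with EEG and ERP terms added, so this points towards a two-sided test with the indicator fitted to all 60. It does not prove it.

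**What that indicator would estimate.** Coded 1 for rIFG and 0 otherwise, with equal arms:

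rIFG − (sham + IOFC)/2 = (rIFG − sham) − 0.5×(IOFC − sham).

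This equals the effect against sham only if the other montage does nothing to that outcome, which the plan does not state. The two montages share a site: FP1 is the cathode for rIFG and the anode for IOFC. As an illustration (my assumption), let rIFG v sham be d=0.35 and let IOFC stimulation have half that effect on the stop-signal task. The tested quantity is then 0.35 − 0.5×0.175 = 0.2625, with power 56%. An opposite effect would inflate it.

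**What would make two-sided 20 v 20 reach 0.35?** The MDE scales with the SD of change, so the variance must fall to (0.35/0.407)² ≈ 0.74 of its value, or (0.35/0.403)² ≈ 0.75 with the three-arm error term. That needs ρ of about 0.925, or covariates explaining about 25–26% of the variance of change. Otherwise 27 per arm (3×27 = 81) are needed: power 80.6%, against 79.0% with 26.

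**The case against.** The strongest reply is that no arithmetic error has been shown. The stated 0.35 can be recovered from a one-sided test of active v sham: 0.358 on change scores, 0.352 by normal approximation, 0.349 with baseline as an ANCOVA covariate. The n=60 in the footnote follows the Aim 2 correlation and does not settle the sample behind d. Sham is plainly the design's control, since the protocol describes a sham procedure and repeats the tasks after tDCS or sham. ANCOVA would also soften the two-sided shortfall, to an MDE of 0.397 and 69.6% power. The gap is small beside the plan's dependence on ρ=0.9: at ρ=0.8 the 20 v 20 MDE would be about 0.57.

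Much of this stands. Pooling the other active arm with sham is an inference, and the shortfall is conditional on a two-sided test against sham. But the plan names repeated-measures ANOVA, for which 0.40–0.41 is the right range, and ANCOVA still leaves about 70% power. A one-sided test would need to be stated, and it does not fit r=0.35 under the same error level. That sham is the design control does not make it the reference group of a model that never mentions it.

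**Conclusion.** The concern holds. The comparator and sidedness behind d=0.35 are unstated, and they determine what the figure means. For a two-sided 5% test of active v sham, the MDE is 0.40–0.41 and power at d=0.35 is 67–68%, about 12 points below the stated 80%. If the indicator is fitted to all 60, the MDE of 0.35 is right, but for a contrast that mixes in half of the other montage's effect.

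These figures rest on ρ=0.9, complete data, change-score analysis, and no variance explained by PROMIS or Conners-3. This should be fixed before analysis, so that neither comparator nor sidedness can be chosen after the data are seen. The design itself can stand.

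**What to change.** - Replace the single indicators in rows H1 and EH1 with a three-level arm factor (rIFG, IOFC, sham) by time, keeping the planned covariates.
- Test H1 as rIFG v sham and EH1 as IOFC v sham, by planned two-sided 5% contrasts using the error variance from all 60. Carry the same coding into H2 and EH2.
- In footnote ‡, state the comparator, the sidedness and 20 per group, and restate d in both rows as about 0.40–0.41.
- Label any active v active comparison as secondary.

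If a one-sided test or a pooled reference group was intended, the plan should say so, justify it, and match the MDE to it.

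The cost is new wording in the table rows and one footnote, and a slightly less favourable MDE. No participants or procedures are added.
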